5.5 Replacement of individual participants after withdrawal

After withdrawal of an individual participant he or she will be replaced depending on the moment of withdrawal.

5.6 Premature termination of the study

Not applicable.

6. SAFETY REPORTING

6.1 Section 10 WMO event

In accordance to section 10, subsection 1, of the WMO, the investigator will inform the participants and the reviewing research ethics committee if anything occurs, on the basis of which it appears that the disadvantages of participation may be significantly greater than was foreseen in the research proposal. The study will be suspended pending further review by

the research ethics committee, except insofar as suspension would jeopardise the participants' health. The investigator will take care that all participants are kept informed.

6.1.1 Adverse events (AEs) and Serious adverse events (SAEs)

SAEs directly related to one of the interventions (venepuncture, nasopharyngeal or oropharyngeal swab) will be registered. Only these SAEs will be registered, as this is a non-interventional, low risk, observational study. AEs directly related to one of the interventions (for example a nose bleed after a nose swab or bruise after a blood test) will not be registered.

6.1.2 Suspected unexpected serious adverse reactions (SUSAR)

NA

6.1.3 Annual safety report

NA

6.2 Follow-up of adverse events

All AEs and SAEs will be followed until they have abated, or until a stable situation has been reached. Depending on the event, follow up may require additional tests or medical procedures as indicated, and/or referral to the general physician or a medical specialist. SAEs need to be reported till end of study within the Netherlands, as defined in the protocol. The investigator will report the SAEs through the web portal *ToetsingOnline* to the accredited METC that approved the protocol, within 7 days of first knowledge for SAEs that result in death or are life threatening followed by a period of maximum of 8 days to complete the initial preliminary report. All other SAEs will be reported within a period of maximum 15 days after the investigator has first knowledge of the serious adverse events. As mentioned in section 6.1.1, only SAE directly related to one of the interventions will be registered.

6.3 Data Safety Monitoring Board (DSMB)

No Data Safety Monitoring Board is needed. However, there will be 3 Advisory Boards, which will act as consultative bodies for ethical, scientific and technical matters.

The following advisory boards will be formed by external experts:

- International Scientific Advisory Group (ISAG)
- RESCEU Ethics Advisory Committee (EAC)
- RESCEU Patient Advisory Board (PAB).

See also appendix 1 for a detailed description of the governance structure of RESCEU.

7. STATISTICAL ANALYSIS

Descriptive statistics will be used to describe the incidence rate of hospitalization for RSV and MA-RSV infection in the cohort of older adults. Demographic parameters, clinical parameters and outcome and laboratory test results will be displayed as categorical data with percentages or continuous variables with mean (+/-SD) and/or median (interquartile range).

Comparisons between groups will be performed using chi-square for categorical variables, Student-t-test for normally distributed continuous variables or Mann-Whitney U test for not normally distributed continuous variables. Multivariate regression analysis will be performed to analyse multiple risk factors for RSV disease.

Statistical analyses will be performed using SPSS version 20 or a more recent version or with R statistical software version 3.0.1 or higher.

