A blood sample (60 ml) and a nasopharyngeal swab will be collected at the beginning (August/September) and end (May/June) of the RSV season. The drawing of blood can be moderately painful. The collection of a nasopharyngeal swab can cause a brief moment of discomfort. Participants will be asked weekly by telephone (verbal or text message), email or telephone app about any signs of respiratory tract infections. In the event of an ARTI two nasopharyngeal and one oropharyngeal swab will be collected to perform a direct reverse transcriptase polymerase chain reaction (RT-PCR) for RSV and additional analyses if RT-PCR is positive for RSV. If a participant experiences a RSV positive ARTI, blood will be drawn (60 ml) and a nasopharyngeal swab will be collected at the time of the infection and 1-2 weeks after onset of symptoms. During the course of each ARTI, independent of RSV status, participants will be asked to complete a short daily diary in order to score respiratory symptoms and quality of life. At inclusion and after approximately one year (+/- 2 months, at least after the RSV season) participants are asked to fill in a short questionnaire.

None of the RESCEU study procedures is associated with any risk for serious complications. However, there is a minimal risk of minor complications due to study procedures (for example a nose bleed after a nasopharyngeal swab or bruise after a blood test).

Possible benefit: There is no clear clinical benefit for the participants taking part in this proposed study. However, the results of this study aim to support the understanding of the burden of RSV disease, which is important for the implication of future preventive and therapeutic interventions.

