3. STUDY DESIGN

[figure not shown]
This will be a multi-country, multicenter, prospective, observational cohort study conducted across 2 consecutive winter seasons to determine the incidence of RSV infection, RSV associated MA-ARTI and RSV related hospitalization in participants ≥60 years of age, recruited from the general population.

These older adults will be recruited from general practitioner (GP) networks between May and October of each year for 2 consecutive years based on pre-specified selection criteria (see section 4.2 and 4.3). Practice lists will be screened for potentially eligible participants. They will be informed by their GP about the study. If they consent that their contact details can be given to the study team, interested potential participants will be contacted by a member of the study team who will answer any questions they may have about the study. When participants are willing to be enrolled in the study, an inclusion visit is booked at the beginning of the RSV season (August/September). During the same visit a blood sample and a nasopharyngeal sample will be collected and a baseline questionnaire about demographic data, medical history, smoking habits and quality of life will be completed.

During the RSV season (October 1st to May 1st, or longer if RSV is still circulating, based on country specific surveillance reports), respiratory tract symptoms will be assessed weekly by telephone contact (verbal or text message), email, (daily) telephone app or online questionnaire. If the participant experiences an ARTI, the study team will visit the participant to collect two nasopharyngeal and one oropharyngeal sample for direct RSV RT-PCR and additional analyses. If RSV is positive a blood sample and nasopharyngeal sample will be obtained at the time of infection and an additional blood and nasopharyngeal sample will be collected 1-2 weeks after the onset of symptoms. At the end of the RSV season (May/June) another blood and nasopharyngeal sample will be collected. Individual participants will be followed up for one RSV season. After approximately one year (+/-2 months) participants will be asked to fill in a questionnaire to finalize follow-up. This questionnaire is about, but not limited to, respiratory disease in the past year, changes in living conditions, health status, frailty and quality of life.

An overview of the study design and main procedures is given below (Figure 2).

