5.1.2 Secondary study parameters/endpoints

- The incidence rate of all-cause MA-ARTI or events leading to worsening of cardiorespiratory status. The incidence rate will also be summarized separately for outpatient events and for both inpatient and outpatient events combined through the RSV season of follow up. Subgroup analyses will summarize these endpoints by RSV season.
- 2. Mortality through the RSV season of follow up for RSV-associated deaths and all cause deaths.
- 3. Health care costs and resource use for RSV-associated and all-cause MA-ARTI (inpatient or outpatient) or events leading to worsening cardiorespiratory status with regard to hospital duration, incidence and duration of intensive care unit stay, supplemental oxygen use, antibiotic and antiviral use and number of outpatient visits (e.g., ER visit, physician office/outpatient visits) and HRQoL.
- The incidence rate of RSV-associated secondary bacterial pneumonia events (defined as pneumonia within 21 days after RSV infection) and associated antibiotic use will be summarized.
- 5. Change in frailty over the course of study.
- 6. Sample collection for biomarker analysis to investigate possible biomarkers which are predictive of severe or complicated RSV disease in older adults. With these

clinical samples a biobank will be established for identifying potential biomarkers of RSV disease severity for further validation.

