5.3 Study procedures

1. Inclusion Visit (August/September)

At the inclusion visit, after eligibility has been confirmed and fully informed consent completed, the following procedures will take place:

- A baseline questionnaire about, but not limited to, demographic data, medical history, risk factors for RSV disease and quality of life will be completed.
- A blood sample (60 ml) and a nasopharyngeal sample will be collected.
- 2. Throughout the RSV season (October 1st to May 1st, or longer if RSV is still circulating based on national viral surveillance programs):

Participants will be asked about respiratory symptoms during the RSV winter season by weekly contact by telephone (verbally or text message), email, telephone app or online questionnaire. If they experience an ARTI, participants are instructed to contact the study team. Two nasopharyngeal and one oropharyngeal sample will be collected by home visits (or in the doctor's office when preferred by participant) within 3 days after contact with the study team. One nasopharyngeal sample will be used for direct RSV RT-PCR testing. The other samples will be stored at -80°C. If RSV is positive a blood sample will be drawn (60 ml) and a nasopharyngeal sample will be collected and stored at -80°C. In addition, in case of a RSV ARTI, 1-2 weeks after onset of symptoms another blood sample (30ml) and nasopharyngeal sample will be collected. During the episode of respiratory disease, participants are asked to complete a diary on respiratory symptoms and HRQoL. At the end of the episode, participants are asked to complete a questionnaire on medical resource use, interruption of daily activities and HRQoL. If participants have been admitted to the hospital, a questionnaire about the reason for hospitalization, diagnosis and treatment will be completed by the study team using medical data from the admitted hospital.

- 3. At the end of the RSV Season (May/June)
 - A blood sample (60 ml) and a nasopharyngeal sample will be collected.
- 4. Approximately one year after inclusion (+/- 2 months).
 - A questionnaire about changes in living conditions, health status and quality of life will be completed.

 Table 2. Overview of sampling of older adults study.

Moment of	Sample	Volume	Analysis (minimum
sampling		00 1	amount)
At beginning of RSV	Serum (venous)	20 ml	RSV serology (350-400 μl)
season (Oct.)			Proteome (100 µl)*
	Paxgene (venous)	10 ml	Transcriptome (200 µI)*
	Whole blood	30 ml	DNA/GWAS (200 µl)

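### Section 7 names only unadjusted tests for group comparisons, so an HRQoL comparison between ARTI groups would not use the inclusion-visit quality of life that the study already collects

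*Protocol*

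**What the plan says.** Section 7 of the protocol gives the methods for comparing groups in one sentence: "Comparisons between groups will be performed using chi-square for categorical variables, Student-t-test for normally distributed continuous variables", with Mann-Whitney U for continuous data that are not normally distributed. The only model in the section serves a different question: "Multivariate regression analysis will be performed to analyse multiple risk factors for RSV disease". Outcomes are otherwise summarised by percentages, means with SD, or medians with interquartile range.

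Quality of life is recorded several times on the same people:

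- **Inclusion** (Section 3): "a baseline questionnaire about demographic data, medical history, smoking habits and quality of life will be completed".
- **During illness** (Summary): "During the course of each ARTI, independent of RSV status, participants will be asked to complete a short daily diary", covering symptoms and quality of life.
- **End of each episode** (Section 5.3): a questionnaire that includes HRQoL.
- **About one year** (Section 5.3): "A questionnaire about changes in living conditions, health status and quality of life will be completed".

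HRQoL in RSV-associated and all-cause medically attended ARTI is a secondary endpoint (Table 1 and Section 5.1.2). So is frailty, worded as "Change in frailty over the course of study".

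**The concern.** Section 7 does choose a method for group comparisons. Applied to HRQoL, it is an unadjusted t-test or Mann-Whitney test, and regression is assigned elsewhere. This matters in two ways.

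**Confounding.** RSV status is not randomised. Participants whose ARTI proves to be RSV, or who seek care for it, may already have had poorer quality of life. An unadjusted difference in episode scores then mixes that earlier deficit with the effect of the infection. RSV burden is what this study exists to measure.

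**Precision.** The RSV group will be small. Part of the spread in episode scores is stable difference between people, which the inclusion score can remove at no cost.

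**Working it through.** The protocol states no effect size, SD, correlation or power for HRQoL, so there is no figure of its own to reproduce on this point.

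**Inputs from Section 4.4.** About 1,000 enrolled, 10% loss to follow-up, 3.0% expected yearly incidence of medically attended RSV. Followed: 1,000 × 0.90 = 900. Expected cases: 0.03 × 900 = 27.

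**Assumptions, not in the protocol.** Correlation ρ between inclusion and episode HRQoL: 0.3, 0.5, 0.7. Comparison group: 100 to 600 participants with one value each. Difference between the groups at inclusion: δ = 0.2 or 0.4 SD. Outcome SD = 1. Normal approximations, two-sided 5%.

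**Step 1: precision.** SE(ANCOVA) = SE(t-test) × √(1 − ρ²). Take an effect that the t-test detects with 80% power, so effect/SE = 1.960 + 0.842 = 2.802. Adjusted power is Φ(2.802/√(1 − ρ²) − 1.960).

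| ρ | SE ratio | effect/SE after adjustment | power |
|---|---|---|---|
| 0.3 | 0.954 | 2.937 | 84% |
| 0.5 | 0.866 | 3.235 | 90% |
| 0.7 | 0.714 | 3.923 | 97–98% |

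The SE formula holds for groups balanced at baseline. With imbalance δ and a share p of participants in the RSV group, the SE is multiplied by √(1 + p(1 − p)δ²). At δ = 0.4 with 27 against 100, p = 27/127 = 0.213 and the factor is √(1 + 0.167 × 0.16) = 1.013, so little of the gain is lost.

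**Step 2: bias of the unadjusted comparison.** If RSV has no effect, the expected difference in episode scores is ρδ.

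- δ = 0.2: 0.06, 0.10 and 0.14 SD at ρ = 0.3, 0.5 and 0.7.
- δ = 0.4: 0.12, 0.20 and 0.28 SD.

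**Step 3: resulting false-positive rate.** SE = √(1/27 + 1/m), which is 0.217 for m = 100 and 0.197 for m = 600. The rate is P(Z > 1.96 − ρδ/SE) + P(Z < −1.96 − ρδ/SE). For δ = 0.4, ρ = 0.5, m = 100: 0.20/0.217 = 0.922, giving P(Z > 1.038) + P(Z < −2.882) = 0.150 + 0.002 = 15%.

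| ρ | δ = 0.2 | δ = 0.4 |
|---|---|---|
| 0.3 | 6% | 9% |
| 0.5 | 7–8% | 15–17% |
| 0.7 | 10–11% | 25–30% |

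Ranges run over m = 100 to 600. With no baseline difference (δ = 0) the rate is the nominal 5%, and only the precision argument remains.

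**The case against.** The strongest reply is that nothing in Section 7 is wrong as written. The sentence covers comparisons between groups, and the named tests have valid standard errors when each person supplies one value or one change score. The HRQoL objective is to estimate, and no contrast is stated. All-cause ARTI includes RSV, so the two populations in Table 1 are not even separate groups. Models for secondary endpoints are often left to a statistical analysis plan, and none is shown here. The 0.4 SD imbalance and the correlations are assumptions.

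Most of this stands, and it limits the point. It does not remove it: Section 7 names the method for any group comparison that is made, and that method leaves out a covariate already in hand.

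A reader might go further and infer that the planned results ignore each person's baseline and carry wrong error bars. The protocol does not support that:

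- A change in frailty by definition uses the person's earlier value.
- No section says that inclusion and one-year values will be compared as two separate groups of people. Power comparisons of paired with unpaired tests for frailty therefore describe an analysis that nobody has planned.
- No section says that diary days or repeat episodes will be counted as independent people.

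The absence of a named paired or clustered method is a detail usually left to the analysis plan.

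**Conclusion.** The point holds in a limited form. Where HRQoL is compared between ARTI groups, the unadjusted tests named in Section 7 are a weaker choice than a baseline-adjusted comparison, on confounding and on precision. The gain is an SE of 0.95, 0.87 or 0.71 of the t-test's at assumed correlations of 0.3, 0.5 and 0.7. The bias avoided is the correlation times the baseline difference. It could be zero, and it reaches 0.28 SD at the upper end of the values tried.

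These sizes rest on assumed correlations, imbalance and comparison-group size, and on the comparison being made at all. Adjustment removes only the part of earlier ill health that the inclusion score captures; measurement error in that score, or decline between inclusion and the ARTI, would leave some behind. The endpoints concerned are secondary, so this is a minor improvement.

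**What to change.** In Section 7, state that:

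1. HRQoL during or after an ARTI is compared between groups by linear regression (ANCOVA) with the participant's inclusion-visit quality of life as covariate.
2. Participant-clustered (robust) standard errors are used if anyone contributes more than one ARTI episode.
3. Chi-square, Student t and Mann-Whitney U are kept for other comparisons with one observation per participant.

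The cost is two or three sentences. The covariate is already collected from everyone, and the SPSS or R software named in Section 7 fits the model. The protocol names no quality-of-life instrument; a covariate, unlike a change score, does not require the inclusion and episode scores to be on the same scale. The one downside is that a rule for missing inclusion scores must be set in advance.

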4. STUDY POPULATION

4.1 Population (base)

Cohort of approximately 1,000 older adults (≥60 years, including approximately 500 ≥75 years). Participants will be randomly recruited from the database of general practitioners in the following countries: the Netherlands (UMCU), Belgium (UA) and United Kingdom (UOXF).

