4.4 Sample size calculation

For the primary analysis the ratio between cases of RSV-related hospitalizations and number of older adults in the total population will be calculated. In addition, the ratio between the cases of MA-RSV infection and the number of older adults undergoing active surveillance will be calculated.

To estimate the incidence of MA-RSV infection and RSV-related hospitalization at an older age, a prospective cohort of approximately 1,000 older adults ≥60 is followed for 1 year. For sample size calculations a statistic expert of the Julius Support Center was consulted. Assuming a yearly MA-RSV incidence of 3,0% based on literature^{5,9}, a sample size of 800 will produce a two-sided >95% confidence interval with a symmetric half width of 0.01 Version number: 3, July 29th 2019

(Confidence interval formula: Exact, Clopper-Pearson). Accounting for a 10% loss to follow up, approximately 1000 elderly will be included in the cohort.

Patient population	Sites	Outcome	Persons	RSV seasons	Expected Incidence per year (%)	95% Confidence Interval Half-Width (%)
Older Adults (≥ 60 years)	NL, UK, BE	Incidence rate of MA-RSV	1,000	1	3,0 ^{5,9}	1,9 – 5,0

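### Chi-square is the only test named for categorical comparisons, with no exact-test fallback for the sparse tables that RSV-specific outcomes are likely to produce (minor)

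*Protocol*

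**What the plan says.** Section 7 of the protocol covers between-group comparisons in one sentence. For categorical data it reads "Comparisons between groups will be performed using chi-square for categorical variables". For continuous data the same sentence makes the choice conditional: a t-test if the variable is normally distributed, Mann-Whitney if it is not. The categorical rule has no such condition and does not say whether a continuity correction applies.

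Two neighbouring sentences limit the reach of the rule. The main rates are descriptive: "Descriptive statistics will be used to describe the incidence rate of hospitalization for RSV and MA-RSV infection in the cohort of older adults". Risk factors go to a model: "Multivariate regression analysis will be performed to analyse multiple risk factors for RSV disease". Section 7 does not list the groups or outcomes to be compared and gives no significance level for comparisons.

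The expected case count comes from Section 4.4: "Assuming a yearly MA-RSV incidence of 3,0% based on literature", and "Accounting for a 10% loss to follow up, approximately 1000 elderly will be included in the cohort". The only group split with stated sizes is by age, in Section 4.1: "Cohort of approximately 1,000 older adults (≥60 years, including approximately 500 ≥75 years". Table 1 in Section 2 includes a risk-factor objective broken down by severity and by use of care. Section 5.1.2 lists RSV-associated and all-cause mortality, and secondary bacterial pneumonia after RSV infection, without expected rates.

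**The concern.** The chi-square p-value is a large-sample approximation, and it becomes unreliable when expected cell counts are small. RSV admissions are a subset of medically attended RSV cases, and RSV deaths and secondary pneumonias arise only among RSV infections. With some 27 to 30 medically attended cases expected, tables of these events against a baseline characteristic are likely to be sparse.

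If the sentence is followed literally, one or two exposed cases can make a characteristic look associated with RSV hospitalisation when an exact test would not support it. Because the correction is left open, two analysts who both follow the protocol could also reach opposite conclusions from the same table.

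**Working it through.** **The plan's own figures.** The protocol gives no expected cell count and no false-positive rate, so there is nothing to reproduce on this point directly. The usable input is the 3.0% incidence in Section 4.4:

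- 0.03 × 1,000 = 30 cases with no loss;
- 1,000 × (1 − 0.10) = 900 followed, and 0.03 × 900 = 27 cases.

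**When is a table sparse?** The smallest expected count is (events × size of smaller group) / N.

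- *Age split, 500 vs 500:* events / 2, which is below 5 with fewer than 10 events.
- *Within 27 RSV cases:* the smaller group is at most 13. Ten admissions give 10 × 13 / 27 = 4.8 and eleven give 11 × 13 / 27 = 5.3. At least 11 of 27 cases must be admitted before every expected count can reach 5.

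**Size of the test.** Assumptions: N = 900, two-sided 5% level, uncorrected Pearson chi-square. Given the total number of events, the number exposed is hypergeometric under no association. The size is the summed probability of the tables with p < 0.05.

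| Events | Exposed share | Uncorrected chi-square | Continuity-corrected | Fisher |
|---|---|---|---|---|
| 3 | 5% | 14.3% | 0.7% | 0.7% |
| 3 | 10% | 2.8% | 2.8% | 2.8% |
| 3 | 20% | 10.4% | 0.8% | 0.8% |
| 3 | 50% | 0% | 0% | 0% |
| 4 | 5% | 1.4% | 1.4% | 1.4% |
| 5 | 5% | 2.2% | 2.2% | 2.2% |
| 5 | 10% | 8.1% | 0.8% | 0.8% |

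The first row shows the mechanism. With 3 events and 45 exposed, a single exposed event already gives p = 0.024, so the size is 1 − P(none exposed) = 1 − 0.857 = 14.3%. With 4 events a single exposed event gives p = 0.066 and no longer rejects, and the size falls to 1.4%. With 27 events, exposures from 5% to 50% give 4.1% to 5.3%, so the test is adequate there.

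**One table by four methods.** Five admissions among 900, 2 of them among the 90 exposed: a = 2, b = 88, c = 3, d = 807, so ad − bc = 1,614 − 264 = 1,350. The smallest expected count is 5 × 90 / 900 = 0.5.

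- Uncorrected: 900 × 1,350² / (90 × 810 × 5 × 895) = 5.03, p = 0.025.
- Continuity-corrected: 900 × (1,350 − 450)² / (90 × 810 × 5 × 895) = 2.23, p = 0.135.
- Fisher: P(2 or more exposed) = 0.0726 + 0.0079 + 0.0004 = 0.081. Zero or one exposed are both more probable than two, so this is also the two-sided value.
- Mid-p: 0.081 − 0.0726 / 2 = 0.045.

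Mid-p therefore rejects the same table as the uncorrected test, and its size with 5 events at 10% exposure is also 8.1%.

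**How typical are the high values?** For N = 1,000, smaller groups of 30 to 500 and 1 to 15 events, the median conditional size of the uncorrected test is 4.1%; 37% of scenarios exceed 5% and 4% exceed 10%. Averaged over a random event count, the largest size found is about 9.3% (30 vs 970, 5 events expected). For 500 vs 500 it is at most about 4.6%.

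**The case against.** The strongest reply is that an exact-test fallback is normally left to a statistical analysis plan, which is not shown here, and that Section 7 is only an outline. This has weight and keeps the point minor. It does not remove it: the sentence names one test without condition, next to a conditional rule for continuous data, so the protocol settles the matter rather than leaving it open.

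A reader might infer that the protocol orders chi-square tests of hospitalisation, death and pneumonia. The documents do not support that. Hospitalisation incidence is descriptive, pneumonia is to be summarised, mortality is listed with no group comparison ("Mortality through the RSV season of follow up for RSV-associated deaths and all cause deaths"), and multiple risk factors go to regression. What remains is that the general sentence excludes no outcome, and the objective on risk factors by severity and use of care invites such tables.

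A reader might also take 14% as the study's false-positive rate, or as its ceiling. It is neither. It is a high point in an erratic pattern, with 0% to 3% at neighbouring margins. A single event at 20% exposure gives 20%. The inflation also presupposes the uncorrected test: with the correction, the three inflated rows of the table fall to 0.7% to 0.8%. That objection is sound as to size, but it confirms that the unstated choice of variant can decide the result.

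Finally, sparse cells are not certain. No rates are given for these outcomes, and all-cause deaths could be more frequent than RSV-specific ones.

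**Conclusion.** The point holds as a minor one. Section 7 fixes chi-square for every categorical comparison without a sparse-table exception or a statement on correction, and the protocol's own 3% incidence makes expected counts below 5 likely for RSV-specific outcomes and for subgroups of RSV cases. In such tables the uncorrected test can be far above or far below its nominal level: 0% to about 14%, conditional on 3 to 5 events, on the exposure shares examined. The same table can be significant or not depending on the variant chosen.

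This rests on an assumed 5% level, an assumed 900 participants followed, assumed event counts and exposure shares, and the inference that RSV-specific events will be few. It does not affect the primary incidence estimates, and comparisons based on all 27 or so medically attended cases in the cohort are adequately served by chi-square.

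**What to change.** Replace the categorical part of the sentence in Section 7 with: *chi-square test, or Fisher's exact test when any expected cell count is below 5*. Add that sparse outcomes will be reported with exact confidence intervals, in keeping with the Clopper-Pearson interval already named in Section 4.4. State whether chi-square is continuity-corrected where it is still used. Do not offer mid-p as the fallback, since it does not hold the 5% level in these tables.

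The change needs no new data, and both packages named in Section 7 provide the test. The cost is conservatism: in sparse tables Fisher's test often runs well below 5% (0.8% with 5 events at 10% exposure), so some real differences will be missed. That is a further reason to put the exact intervals, rather than the p-values, first.
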